Figure 2 provides a general framework of the study design. This 12-week clinical study involves the testing and training of middle age to older (40 - 75 y), overweight or obese adults (BMI 26 - 44 kg/m²) with type 2 diabetes (T2DM). Sixty subjects will be randomized to 12 weeks of aerobic exercise training plus standard care (Aerobic Exercise group; n=30) or standard care only (Control group; n=30). Subjects randomized to the Control group will be given the option of an off-label exercise intervention. Therefore, Control group participants will be allowed to enroll in the AE training group after completion of the original Control group trial period. All subjects will undergo the same baseline and post testing for basal metabolic rate, maximal aerobic capacity (VO₂max), body composition, insulin sensitivity, and microdialysis sampling coupled with muscle biopsies during an acute aerobic exercise trial before.

Due to the complexity of this study, an interdisciplinary research team with experience in clinical trials, pathophysiology of, and research in obesity, insulin resistance and T2DM, vascular function, aerobic exercise testing/training, clinical medicine, biotechnology, and advanced biostatistics has been assembled. The research staff has many years (>10 y) of direct research experience with human subjects and have been trained by experts in the field and University of Michigan protocols and guidelines.

Primary Outcome Measure

1) Quantify the change in basal circulating sRAGE after 12-weeks of supervised aerobic exercise training.

Serum will be separated from blood samples collected in vacutainer tubes via centrifugation before and after 12-weeks of aerobic exercise training. sRAGE will be quantified in these serum samples via ELISA (Quantikine, Human RAGE Immunoassay) per manufacture's protocol.

Secondary Outcome Measures

1) Quantify the change in basal muscle RAGE expression after 12-weeks of supervised aerobic exercise training.

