A total of 60 adults, (approximately 30 males and 30 females) will complete this study. Subjects must be weight stable (± 2 kg for ≥ 6 months), sedentary (<30 min of exercise, 3 times per week), and free of any additional contraindications to participation in exercise testing or the training. Selection criteria will limit confounding influence on the study objectives and exclude subjects with conditions that may have unknown effects on metabolic function and the outcomes proposed or the ability to participate in the aerobic exercise intervention or testing procedures. Criteria will be reviewed by the research team and/or study physician and eligibility to participate will be determined on a case by case basis.

Subject Inclusion Criteria

- Age 40-75 y
- Type 2 diabetes
- Overweight or obese (BMI 26-44 kg/m²)
- Fluency in English (written and verbal)

Subject Exclusion Criteria

- Age <40 or >75 y
- BMI <26 or >44 kg/m²
- Existing cardiovascular, cerebrovascular, renal, or hematological disease, cancer, or other metabolic diseases that is suspected to impact study outcomes
- Current use of tobacco
- Pregnant or lactating

Strategies for Recruitment and Retention

Subjects will be recruited from the greater Ann Arbor area through multiple mechanisms. Primarily, study advertisements will be posted and distributed throughout the communities surrounding the University of Michigan. In addition, we will utilize our clinical collaborations within the Division of Endocrinology and Metabolism to strengthen our ability to identify and recruit potential volunteers. We plan to advertise and seek potential volunteers through word of mouth, the Data Office for Clinical and Translational Research, MDRC Diabetes Research Registry, the website of the School of Kinesiology, newspaper, postal mail, and social media outlets. In our previous studies, we have not experienced difficulty recruiting individuals for muscle biopsy or metabolic procedures.

Screening Procedures

Initial screening of participants will occur via a website screening tool or telephone interview. During this time, the study will be described in detail and we will obtain information about age, body mass index (BMI), smoking and physical activity status, current medical conditions, health status and medications, along with other eligibility

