criteria. Subjects who meet the initial screening criteria will be scheduled for a complete screening at the Michigan Clinical Research Unit (MCRU), Frankel Cardiovascular Center (CVC), Domino Farms, or the Central Campus Recreation Building (CCRB). At this time, more specific details about the study will be provided along with answers to any questions. Each study procedure and all possible risks related to these procedures will be explained along with sample exercise programs and explanation of the randomization methods of the study. Verbal and written informed consent will be obtained during this initial visit according to the guidelines of our Institutional Review Board. A study team member will perform a comprehensive medical history. Additionally, participants will complete a venipuncture blood draw and urine collection for laboratory assessment of complete blood count (CBCD), comprehensive metabolic panel (COMP), urinary analysis (UA), urinary microalbumin (UMA), hemoglobin A1C (A1C), thyroid stimulating hormone (TSH), and lipid panel. Females will also be asked to provide urine for a pregnancy test (for premenopausal women). In addition, participants will complete a supervised 12-lead resting electrocardiogram and graded exercise stress test (with VO₂) at the CVC or Domino Farms. EKG test results will be reviewed by a study physician. If any blood work or EKG results are clinically significant, the participant will be notified and referred to their personal physician for additional evaluation prior to further consideration for participation in this study. Baseline food intake will be assessed from diet history including multiple replicate 24-hour recalls to estimate usual intake, customary eating pattern, and food frequency questionnaires. After confirmation of the participant meeting all inclusion and exclusion criteria, participants will be enrolled into the study intervention.

STUDY INTERVENTION

Intervention Description

This study's intervention includes 12 weeks (± 1 week) of supervised aerobic exercise training for the group randomized to Aerobic Exercise. The Control group will not be subject to an intervention as they will receive standard care only (see *Standard Care*). Subjects randomized to the Control group will be given the option of an off-label exercise intervention. Therefore, Control group participants will be allowed to enroll in the AE training group after completion of the original Control group trial period.

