Group Assignment Procedure

Following enrollment into the study, participants will be randomized into either the Aerobic Exercise group (n=30) or Control group (n=30. Females and males will be equally distributed between the groups. Regardless of group assignment, each participant will receive standard care for diabetes management.

Aerobic Exercise Training

Every AE training session will be supervised by the research team using established protocols [22-28]. Training sessions will take place at the Central Campus Recreation Building (CCRB), Domino Farms, or other University of Michigan recreation facility (e.g., North Campus Recreation Building) approximately 5 days per week and include treadmill walking, cycling, elliptical, or other related modes of exercise. Briefly, AE training will begin with a 2-week ramp-up, familiarization period of progressing exercise intensity and duration. Training intensity will progress from 55% VO₂max for week 1 (40 min session), to 60-65% VO₂max for week 2 (50 min session), to ~70% VO₂max for all other weeks (50 min session). Subjects will perform a brief warm-up and cool-down (~5 min each) that may include stretching or other light exercises for a total exercise time of 60 min. Subjects will wear heart rate monitors during each training session to provide real-time feedback of target heart rate. Intensity, duration, resting and exercise heart rates, and blood pressures will be recorded for each session. Exercise duration and intensity may be adjusted at the discretion of the PI, Co-I, or study team member. Followup VO₂max tests will be performed at approximately weeks 4 and 8 to monitor progress. AE intensity will be adjusted to match the prescribed training intensity [23, 24, 29-32]. Subjects in the AE training group will also conduct foot safety checks with the research team to monitor foot ulcers/blisters. Relevant findings during foot inspections will be addressed with the participant and study physician. Non-weight bearing exercise may be implemented if the subject is limited.

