The primary outcomes of this study involve collecting data at pre-aerobic exercise training and 12 weeks of training. Comparisons of trajectories across groups (training vs. Control) over time are made with appropriate adjustments for fixed (age, sex, medications, diabetes duration and severity) and time-varying covariates (i.e., weight, BMI, etc). Because of the anticipated nonlinear response curves of outcome variables we will use nonlinear mixed effects models to analyze our data. Using PROC NLMIXED in SAS 9.2 (SAS Inc.) we will fit the nonlinear models using two likelihood-based methods: adaptive Gaussian guadrature and a first-order Taylor series approximation [54-56]. The nonlinear mixed model is: $y = f(x_{ij}, \beta, u_i) + e_{ij}$, where f is some nonlinear function of known vector covariates (xij) for the jth observation on the jth subject, unknown fixed effect parameters (β), an unknown vector of random effect parameters (u_i), and unknown random errors (eii). For this study, we will treat training group as main fixed effect, intercept as random effects, and all outcomes will be used as responsive variables. Using nonlinear mixed effects models described above, we will reject null hypothesis if significant (p<.05) interaction effect between group and time is observed. Post-hoc analysis will examine differences between groups at different time points to assess the effect of exercise training on the outcome variables across time during the intervention. Our human sample size was determined using data from preliminary studies to provide adequate power after attrition to test the hypothesized effect of training on skeletal muscle RAGE and sRAGE concentrations. We will enroll 75 subjects with the anticipation that there will be 20-25% attrition at 12 weeks. We anticipate that the final N after attrition will be 60 (n= 30 per group). Using the two-sided alpha level of 0.05, we estimate that a total sample size of 60 will enable us to detect a pre-post, between-group difference of 1.24 standard units for RAGE between Aerobic Exercise training and Control groups with a target of 90% statistical power.

Safety and Efficacy Review

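### Sixty is given both as the number randomised and as the number left after 20-25% attrition from 75 enrolled; the two agree only if nobody is lost after randomisation

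*Combined protocol and SAP*

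**What the plan says.** All references are to the combined protocol and SAP.

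- *Study Design*: "Sixty subjects will be randomized to 12 weeks of aerobic exercise training plus standard care (Aerobic Exercise group; n=30) or standard care only", again with n=30 in the control arm.
- *Group Assignment Procedure*: "Following enrollment into the study, participants will be randomized into either the Aerobic Exercise group (n=30) or Control group (n=30".
- *Elligibility and Enrollment*: "A total of 60 adults, (approximately 30 males and 30 females) will complete this study".
- *Statistics and Sample Size Considerations*: "We will enroll 75 subjects with the anticipation that there will be 20-25% attrition at 12 weeks", followed by "We anticipate that the final N after attrition will be 60 (n= 30 per group".
- *Screening Procedures*, on the order of events: "After confirmation of the participant meeting all inclusion and exclusion criteria, participants will be enrolled into the study intervention". The opening of *Study Schedule and Procedures* gives the same sequence of screening, enrolment and then randomisation.

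The power statement, at two-sided alpha 0.05 with a 90% target, is that "a total sample size of 60 will enable us to detect a pre-post, between-group difference of 1.24 standard units for RAGE". Just before it, the sample size is said to have been chosen "to test the hypothesized effect of training on skeletal muscle RAGE and sRAGE concentrations". Circulating sRAGE is the primary outcome and muscle RAGE expression is the first secondary outcome.

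**The concern.** The same number, 60 in two groups of 30, does two jobs. In the design and group assignment sections it is the count at randomisation. In the eligibility and sample-size sections it is the count at the end, after a fifth to a quarter have been lost. The power sentence rests on the second meaning.

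What is at stake is when recruitment stops. A team that closed randomisation at 60 would be following the design section, and a team that continued until 75 were enrolled would be following the sample-size section. These lead to different numbers of completers, and only one of them can match the N of 60 used for power.

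There is also a smaller point. Attrition is given as a range, but the expected final N is a single figure that corresponds to one end of it.

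**Working it through.** **Inputs from the plan.** 75 enrolled; 20-25% attrition at 12 weeks; 60 (30 per group) after attrition; 60 (30 + 30) randomised; 1.24 standard units; two-sided alpha 0.05; 90% power. The plan gives no SD and no pre-post correlation.

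**Step 1: the plan's final N.** Completers = starting number × (1 − attrition).

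| Starting number | 20% loss | 25% loss |
|---|---|---|
| 75 | 75 × 0.80 = 60 | 75 × 0.75 = 56.25, so 56 |
| 60 | 60 × 0.80 = 48 | 60 × 0.75 = 45 |

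The stated 60 is reproduced from 75 at 20% loss only. Keeping 60 at 25% loss would need 60 / 0.75 = 80.

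**Step 2: can 60 be both randomised and completing?** Going from 75 enrolled to 60 randomised uses 15 people, and 15/75 = 20%. For 60 then to complete, the whole 20% must be lost between enrolment and randomisation, with none lost during the 12 weeks. At 25% loss it is impossible, because only 56 remain. The 45-48 in the table assumes the opposite extreme, with 60 randomised and all attrition afterwards. A mixture falls between the two.

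**Step 3: the power sentence, as a benchmark.** Unadjusted two-sample t test, noncentral t, df = N − 2, noncentrality = d / √(1/n₁ + 1/n₂).

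*Reading A: 1.24 is in SDs of the 12-week change, so d = 1.24.* With 30 per arm the noncentrality is 1.24 / √(2/30) = 4.80 and power is 99.7%; with 28 per arm it is 99.5%. The difference detectable at 90% power is 0.85 SD (30 per arm) or 0.88 SD (28 per arm). For 1.24, 15 per arm would be enough (90.6%).

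*Reading B: 1.24 is in SDs of a single measurement.* The SD of change is √(2(1 − ρ)) single-measurement SDs, where ρ is the pre-post correlation. At an assumed ρ = 0 this is 1.414. The detectable difference is 0.851 × 1.414 = 1.20 (30 per arm) or 0.882 × 1.414 = 1.25 (28 per arm), which bracket the plan's 1.24. Power at 1.24 is 91.6% and 89.7%.

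**Step 4: the same benchmark if only 60 are randomised and all loss follows.** Every ρ is an assumption.

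| Power at 1.24 | 48 complete | 45 complete |
|---|---|---|
| SD of change | 98.8% | 98.2% |
| Single measurement, ρ = 0 | 84.5% | 82.0% |
| Single measurement, ρ = 0.2 | 91.4% | 89.5% |
| Single measurement, ρ = 0.3 | 94.4% | 93.0% |

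On the single-measurement reading, 90% is reached at ρ of about 0.16 (48 completers) or 0.21 (45 completers).

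**The case against.** The strongest reply is that this is loose wording. The eligibility and sample-size sections agree on 60 completers, the inflation to 75 is written down, and the 30 per arm in the design section matches the group size after attrition. On that view, staff who read the whole document would enrol 75. This is probably the simplest reading, but the design section still says 60 are randomised, so it needs correcting even if the intention was sound. That staff would actually stop at 60 is a possibility, not something the documents establish.

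A second reply is that people may be lost between enrolment and randomisation. Baseline testing is heavy and includes the glucose tolerance test used to confirm diabetes. Attrition at 12 weeks could also mean cumulative loss counted at that point. This stands in part. It narrows the gap, but closes it only if every loss comes before randomisation, which sits poorly with a plan that places randomisation directly after enrolment and dates attrition at 12 weeks. It also means that the sample-size section gives an enrolment number. A reader might infer that it commits to randomising 75; it does not say so.

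Third, 56 against 60 is a small difference, and 60 is offered as an anticipation within the plan's own range. That is fair, and the consequence for power is slight.

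**Conclusion.** The count conflict is established: 60 cannot be both the number randomised and the number completing unless there is no loss after randomisation, and the plan expects 20-25% attrition by week 12. The shortfall is 12 to 15 completers (45-48 instead of 60) if only 60 are randomised and all the attrition follows. The flat 60 holds only at the favourable end of the stated range.

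Three stronger conclusions might be inferred, and the documents support none of them.

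- *The trial is underpowered.* On the change-SD reading, power at 1.24 is about 98% or more even with 45 completers. On the single-measurement reading it falls clearly below 90% only with 60 randomised and a low assumed correlation.
- *The power calculation is wrong.* Measured in SDs of change, 1.24 does not match 60 completers at 90% power. Measured in single-measurement SDs with correlation near zero, it nearly does. The unit is named but not defined, so the sentence cannot be checked; that does not make it false.
- *The only power figure is for the secondary outcome.* The label RAGE may be shorthand for both measures named just before it.

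The power figures here come from an unadjusted t test. The planned analysis is a covariate-adjusted mixed model, so they are benchmarks only.

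**What to change.** State one number enrolled, one randomised and one expected to complete, and use them consistently in *Study Design*, *Elligibility and Enrollment*, *Group Assignment Procedure* and *Statistics and Sample Size Considerations*. The sponsor must say which meaning was intended.

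- *If the sample-size section governs*, as its attrition dated at 12 weeks suggests: the design and group assignment sections should say that about 75 are randomised (37-38 per arm), with 30 per arm described as the completer target. The sample-size section should give 56-60 expected completers.
- *If 60 randomised was meant*: restate the expected completers and the N in the power sentence as 45-48, or as the number left after whatever part of the 20-25% falls after randomisation.

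When restating the power sentence, define standard units as the SD of change or the single-measurement SD, give the pre-post correlation used, and name the analysis behind the figure. Say whether RAGE means muscle RAGE or circulating sRAGE; if it means muscle RAGE only, add the matching statement for the primary outcome.

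Under the first option the cost is wording and a slightly less favourable stated N, with no one beyond the 75 already planned for enrolment. If the sponsor had in fact meant to randomise 60, moving to 75 would add 15 randomised participants and would not be a wording change. Guaranteeing 60 completers at 25% loss would take 80, five more than planned; nothing here requires it. The unit, correlation and outcome must come from the sponsor's preliminary data.
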